## 5.2 Visit Procedures and Visit Windows

Please refer to the protocol for the trial in which subjects are concurrently enrolled for a full list of visit procedures. Procedures and visits required for P11-4 are listed below and presented in [Figure 1](#) and [Appendix 1](#). The permitted window for visits for P11-4 is  $\pm 1$  week with the exception of baseline for the purposes of P11-4 sample collection, which occurs any time after informed consent for P11-4, but  $\leq 28$  days prior to leukapheresis for the first dose of sipuleucel-T.

### 5.2.1 Enrollment

Prior to consenting to enroll in P11-4, subjects must have consented to participate in a concurrent trial in which they may receive sipuleucel-T, and must sign the informed consent form (ICF) for P11-4 before any leukapheresis procedures are performed for preparation of sipuleucel-T, and before any blood samples for P11-4 are collected ([Figure 1](#), [Appendix 1](#)). The process for obtaining informed consent for P11-4 is described in [Section 9.4](#).

### 5.2.2 Registration

After signing the ICF for P11-4, subjects must be registered in the trial as outlined in the site reference manual.

### 5.2.3 Baseline Demographics and Disease Characteristics

Baseline for demographics and disease characteristics will be defined as the last known visit for the concurrent trial prior to leukapheresis for the first dose of sipuleucel-T.

For subjects concurrently enrolled in an IIT, baseline demographics and disease characteristics, including age/date of birth, height, weight, race, ethnicity, Eastern Cooperative Oncology Group (ECOG) Performance Status, Gleason score, prior prostate cancer treatment (yes/no), alkaline phosphatase, lactate dehydrogenase (LDH), serum PSA, hemoglobin, presence of visceral

metastases, number of bone metastases (0, 1-5, 6-10, or >10), and localization of disease (bone vs soft tissue) will be collected ([Appendix 1](#)).

Collection of baseline demographics and disease characteristics will not be required for P11-4 subjects who are concurrently enrolled in a Dendreon-sponsored trial or registry, as this information will be available in the database of the respective trial.

#### **5.2.4 Sipuleucel-T Treatment**

The date and lot number of each sipuleucel-T infusion will be recorded for subjects concurrently enrolled in an IIT ([Appendix 1](#)). Collection of sipuleucel-T infusion date and lot number will not be required for P11-4 subjects who are concurrently enrolled in a Dendreon-sponsored trial or registry, as this information will be available in the database of the respective trial or registry.

#### **5.2.5 Immune Monitoring and Additional Optional Research**

When providing consent to participate in this study, subjects will be given the option to consent to:

- Sampling for product characterization, immune monitoring, and other testing, with retention of samples by Dendreon or designee for up to 5 years, or
- Sampling for product characterization, immune monitoring, AOR, and other additional testing, with retention of samples by Dendreon or designee indefinitely.

##### **5.2.5.1 Immune Monitoring**

Blood samples for immune monitoring (60 mL) will be collected at baseline and 6, 10, 14, 26, 39, and 52 weeks after the first sipuleucel-T infusion ([Figure 1](#), [Appendix 1](#)). If, for any reason, leukapheresis or sipuleucel-T infusion will occur on the same day as blood samples are to be drawn for immune monitoring, the immune monitoring sample will be obtained prior to leukapheresis or sipuleucel-T infusion.

##### **5.2.5.2 Additional Optional Research**

Subjects in this trial will be given the opportunity to consent to allow Dendreon to collect investigational blood samples for use in AOR, which will include both genomic and gene expression analyses, and other additional testing (e.g., human leukocyte antigen [HLA] phenotyping or protein array). Blood samples for AOR will be collected from only those subjects who agree to allow Dendreon to conduct these analyses.

For genomic analyses, an additional, 8.5 mL blood sample will be collected in a specialized tube containing an additive that stabilizes DNA (e.g., PAXgene® Blood DNA tube) one time only, either at baseline (preferred) or at any one of the other immune monitoring time points (6, 10, 14, 26, 39, or 52 weeks after the first infusion of sipuleucel-T). For gene expression analyses, an additional, 2.5 mL blood sample will be collected in a specialized tube containing an additive that stabilizes RNA (e.g., PAXgene Blood RNA tube) at all immune monitoring time points (baseline [any time after informed consent for P11-4, but  $\leq$  28 days prior to leukapheresis for the first dose of sipuleucel-T] and 6, 10, 14, 26, 39, and 52 weeks after the first infusion of sipuleucel-T). Gene expression analyses will be performed by Dendreon or designee.

If, for any reason, leukapheresis or sipuleucel-T infusion will occur on the same day as blood samples are to be drawn for AOR, the AOR samples will be obtained prior to leukapheresis or sipuleucel-T infusion.

### 5.3 Sample Retention

For subjects who consent to participate in P11-4, samples obtained for product characterization, immune monitoring, and other testing will be retained for up to 5 years following Dendreon's completion of this trial and then destroyed, except for subjects who provide additional consent for AOR.

For P11-4 subjects who provide additional consent for AOR, Dendreon or its designee may retain samples obtained for product characterization, immune monitoring, AOR, and other additional testing indefinitely.

Retained samples will be used for research only, will not be sold, and will not be identified using subject names or other personal identifiers.

Samples retained for immune monitoring or AOR may be sent to outside laboratories for testing. These samples will not be identified using patient names or other personal identifiers.

For subjects concurrently enrolled in a Dendreon-sponsored trial or registry, neither the subject nor the trial site will receive immune monitoring, AOR, or other test results. For subjects concurrently enrolled in an IIT, test results will be provided to the Principal Investigator or site for research purposes only and only as pre-specified in the approved IIT protocol. For these subjects, test results will not be released for clinical use, or for any use not specified in the approved IIT protocol.

## **6.0 SUBJECT SELECTION**

### **6.1 Subject Eligibility**

All men with prostate cancer aged  $\geq 18$  years who are enrolled in a Dendreon-sponsored trial or registry, or an IIT and will receive sipuleucel-T are eligible to participate in this trial if they have not yet undergone leukapheresis for their first dose of sipuleucel-T.

### **6.2 Removal of Subjects from Assessment**

Whenever possible, subjects should remain on study. The investigator may withdraw a subject from assessment if, in his or her clinical judgment, it is in the best interests of the subject.

Subjects may discontinue their participation in the trial at any time without prejudice, and without affecting eligibility for the trial in which they are concurrently enrolled.

Participation in this study may end prior to the collection of the week 52 blood sample(s), if the subject withdraws from, or otherwise completes participation in, the concurrent trial.

At the time of withdrawal from the trial, subjects have the right to request that any samples not yet analyzed be destroyed.

## **7.0 STATISTICAL CONSIDERATIONS**

### **7.1 Methods**

#### **7.1.1 Immune Response Variables**

The immune response will be assessed with the following assays:

- T cell IFN- $\gamma$  ELISPOT response to PA2024 and PAP
- T cell proliferation response to PA2024 and PAP by H-thymidine uptake
- Humoral response to PA2024 and PAP by ELISA

A subject will be declared a responder for a particular assay if the observed result is greater than a threshold value, where the threshold value is determined from all responses measured at baseline that ensures a sufficiently low false positive rate (i.e., 5% or less).

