## **2.0 STUDY OBJECTIVES**

### **2.1 Primary Objective**

To evaluate the immune response induced by sipuleucel-T

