## **3.0 STUDY ENDPOINTS**

### **3.1 Primary Endpoint**

The percentage of subjects who exhibit any immune response at any post-treatment timepoint (6, 10, 14, 26, 39, and 52 weeks after the first infusion of sipuleucel-T) on the basis of:

- Interferon-gamma (IFN $\gamma$ ) enzyme-linked immunospot (ELISPOT) response to PAP or PA2024
- T cell proliferation response to PAP or PA2024
- Anti-PAP or anti-PA2024 humoral response

Antigen-specific T cell responses will be assessed using assays such as, but not limited to, H-thymidine uptake to measure the capacity of T cells to proliferate in response to antigen

stimulation, and IFN $\gamma$  ELISPOT. The functional phenotypes of T cell subsets will be investigated using polychromatic flow cytometric analysis. Antigen-specific humoral responses will be measured using techniques such as enzyme-linked immunosorbent assay (ELISA).

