## **4.0 STUDY TREATMENT**

All subjects who participate in this study will receive sipuleucel-T, and will potentially receive other medications as part of the trial in which they are concurrently enrolled; no additional study treatments will be required for this study. Each dose of sipuleucel-T is prepared using cells from a single leukapheresis procedure. A complete course of sipuleucel-T therapy consists of 3 doses of sipuleucel-T administered via intravenous (IV) infusion at approximately 2-week intervals. Please refer to the sipuleucel-T Package Insert or Investigator's Brochure for specific product information.

[figure not shown]

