## 7.2 Statistical Analysis

### 7.2.1 Primary Analysis

The primary endpoint is the percentage of subjects who exhibit an immune response at any post-treatment time point (6, 10, 14, 26, 39, and 52 weeks after the first infusion of sipuleucel-T). The primary immune response analysis population will include all subjects who receive all 3 infusions of sipuleucel-T; summaries will also be generated for the population of patients who receive at least one partial infusion of sipuleucel-T. Logistic regression will be used to explore the effect of baseline characteristics on the primary endpoint. Repeated measurement mixed models will be used to explore the individual immune response assays as continuous endpoints over time. Transformation of the continuous outcome may be applied if the original data are not normally distributed. Key subgroups of interest will be defined on the basis of baseline demographics and disease characteristics (e.g., age, race, ECOG status, and serum PSA).

Table 1 summarizes the minimum detectable percent difference in immune responders with 90% power using a two independent proportions test at the two-sided 0.05-level between two subgroups, with the smaller subgroup representing 10% of total sample size and a minimum immune response incidence in each subgroup of 20% to 80%. In the IMPACT study, 79% of sipuleucel-T subjects had an immune response by any of the 3 assays to either PA2024 or PAP at any time point post-baseline (Sheikh 2013).

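### The 5% false-positive limit applies to single assay results, not to the any-readout, any-visit primary endpoint, and no composite baseline rate is planned, so the primary percentage alone does not show how much response was induced

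*Combined protocol and SAP*

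**What the plan says.** The primary objective in Section 2.1 is "To evaluate the immune response induced by sipuleucel-T".

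Section 7.1.1 lists three assays (IFN-gamma ELISPOT, T cell proliferation, ELISA), each run against PA2024 and PAP, which makes six readouts. It then gives the rule: "A subject will be declared a responder for a particular assay" when the result exceeds a cut-off, where the "threshold value is determined from all responses measured at baseline that ensures a sufficiently low false positive rate (i.e., 5% or less"). It does not say whether the limit is per assay or per assay-antigen pair, and it says nothing about the composite.

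Section 3.1 defines the endpoint as "The percentage of subjects who exhibit any immune response at any post-treatment timepoint", and Section 7.2.1 repeats it: "The primary endpoint is the percentage of subjects who exhibit an immune response at any post-treatment time point". The visits are weeks 6, 10, 14, 26, 39 and 52.

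Section 5.2.5.1 provides the material for a baseline comparison: "Blood samples for immune monitoring (60 mL) will be collected at baseline" as well as at those six visits. Sections 7.2.1 and 7.2.2 plan no any-readout rate at baseline and no comparison of responder rates with baseline. The synopsis states that the study uses no reference product. Section 7.2.1 does plan repeated-measures mixed models, but for each assay separately as a continuous outcome.

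**The concern.** The false-positive limit and the endpoint are set at different levels. The limit concerns one assay result. The endpoint gives each man up to 6 readouts x 6 visits = 36 chances to be called a responder. Capping each result at 5% does not cap the chance that at least one of many results crosses its cut-off.

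That would matter less if the plan measured the background of the composite, but it does not. All men receive sipuleucel-T, there is no control group, and the any-readout rule is applied only after treatment. The reported percentage therefore combines induced response with background positivity, and no composite background figure stands beside it. The number of chances also varies between men, because Section 6.2 lets participation end before week 52.

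Responder status is also used in the planned logistic models (Sections 7.2.1 and 7.2.2) and Cox models (Section 7.2.2), so what it means matters beyond the single percentage.

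**Working it through.** **The plan's own figures.** The plan states no background or composite false-positive rate, so there is none to reproduce. Table 1 gives detectable differences between subgroups. It reproduces with a pooled two-proportion formula (for example 15.3% against the stated 15% for 900/100 at 20%), but it does not bear on this point.

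**Inputs from the documents.** Per-result limit a = 5% or less (7.1.1). Readouts: 3 x 2 = 6 (7.1.1). Post-treatment visits: 6 (3.1, 7.2.1). Baseline samples per man: 1 (5.2.5.1). The documents give no correlations between readouts or visits, so those below are assumptions.

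**Step 1: range at exactly 5% per result.** If all results are completely dependent, the composite rate is 5%. If k results are independent, it is 1 - 0.95^k:

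- 3 assays, one visit: 1 - 0.95^3 = 14.3%
- 6 readouts, one visit: 1 - 0.95^6 = 26.5%
- 3 assays, six visits: 1 - 0.95^18 = 60.3%
- 6 readouts, six visits: 1 - 0.95^36 = 84.2%

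**Step 2: between the extremes.** A latent-normal simulation was run with 200,000 men, no treatment effect and fixed cut-offs. Each case is labelled by the correlation within a readout across visits, then the correlation between readouts at a visit. Ranges cover two assumptions about different readouts at different visits: correlation equal to the product of the two values, or equal to the between-readout value.

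| Assumed within / between | One visit, 5% | Three visits, 5% | Six visits, 5% | Six visits, 1% |
|---|---|---|---|---|
| 0.5 / 0.2 | about 24% | 45-47% | 59-64% | 21-23% |
| 0.8 / 0.2 | about 24% | 38-39% | 47-49% | 15-16% |
| 0.9 / 0.5 | about 19% | 26-27% | 31-32% | about 10% |
| 0.9 / 0.8 | about 12.5% | 17-19% | 20-23% | 6-7% |

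The 1% column is included because the plan says 5% or less. The three-visit column shows how the figure depends on length of follow-up.

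**Step 3: what a baseline composite can and cannot supply.** Each man has one baseline sample, so the any-of-six rate at baseline matches the any-of-six rate at one later visit (the one-visit column). It does not match the six-visit endpoint.

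Suppose background positivity c is the same at both times and independent of induced response t. The visit rate is then 1 - (1 - c)(1 - t), and visit minus baseline is t(1 - c). A true 50% would show as 0.50 x 0.875 = 44% at c = 12.5%, and as 0.50 x 0.76 = 38% at c = 24%. The net change therefore tends to understate induced response when background is material.

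**Step 4: precision of the paired difference.** With cut-offs treated as fixed, assumed baseline rates of 10-25%, visit rates of 40-60% and within-man phi of 0 to 0.3, the 95% CI half-width is 6.8-9.2 points at n = 200, 4.3-5.8 at 500 and 3.0-4.1 at 1000.

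**Step 5: re-use of baseline data.** Cut-offs set at the empirical 95th percentile of the same baseline samples create a small spurious difference when there is no effect. With six independent readouts it is +1.9 points at n = 200, +0.9 at 500 and +0.4 at 1000. With correlations 0.9/0.5 it is +1.0, +0.4 and +0.2.

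**The case against.** **The unit is not really open.** A reader might infer that the 5% is wholly undefined and could be a limit per man over all visits. The text does not support that. The rule is tied to a particular assay and calibrated on baseline responses, with one baseline draw per man. Per sample and per man coincide at baseline, and a per-man limit over six visits could not be calibrated from one draw. Per result is the natural reading. What remains open is assay versus assay-antigen pair, together with the silence on the composite.

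**A baseline rate would not calibrate the primary percentage.** This stands. A reader might infer that adding the any-of-six baseline rate would separate induced from chance response in the any-visit figure. It would not, because one look is being set against six. The paired comparison is a different and useful quantity, and should be labelled as such.

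**The mixed models already look at change.** They give information on each assay as a continuous value, and background is capped for each assay. They do not calibrate the binary composite.

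**The 79% is well above background.** A reader might go the other way and infer that the 79% quoted in Section 7.2.1 is inflated, since those men "had an immune response by any of the 3 assays to either PA2024 or PAP at any time point" after baseline. The documents support neither inference. They give no cut-off, false-positive rule or visit count for that figure.

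**Nothing is tested.** This is correct. No success criterion rests on the percentage, so there is no inflated error rate to report.

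**Conclusion.** The point holds as one of interpretation, and it should be fixed. The 5% limit does not bound the composite primary endpoint. With no comparator and no composite baseline rate, the primary percentage alone does not show how much of the response was induced by sipuleucel-T.

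The omission is certain from the text; its size is not. At exactly 5% per result and without negative dependence, the composite background lies between 5% and 26.5% at one visit and between 5% and 84% over six visits. The illustrative 20-64% (or 6-23% at 1% per result) rests on assumed correlations and a latent-normal model. A reader might infer that most of the observed responses would be chance positives; the documents do not show that.

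**What to change.** **Section 7.1.1.** State that the 5% applies per readout (assay-antigen pair) per sample, and that it does not apply to the composite.

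**Section 7.2.1.** Apply the same any-of-six-readouts rule, with the same cut-offs, to the baseline sample. Report that rate beside the rate at each visit. In men with both samples, give the paired visit-minus-baseline difference with a 95% CI and the number of men, and call it the net change in the proportion positive.

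Keep the any-visit percentage as the primary endpoint. Note beside it that it can accumulate chance positives over visits, and that the single-visit baseline rate does not give the any-visit chance rate.

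State the limits of the net change. It can understate induced response. It also does not remove assay drift or the effects of other treatment, since men "will potentially receive other medications as part of the trial in which they are concurrently enrolled".

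**Optional sensitivity analysis.** Use cross-validated cut-offs, with a bootstrap that re-derives them. The bias at issue was at most about 2 points in the cases examined, so this need not be mandatory.

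**Cost.** A few sentences and a little more analysis, with no new samples because the baseline blood is already drawn. The downside is a net-change figure that will look less favourable than the any-visit percentage.

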## 7.2 Statistical Analysis

### 7.2.1 Primary Analysis

The primary endpoint is the percentage of subjects who exhibit an immune response at any post-treatment time point (6, 10, 14, 26, 39, and 52 weeks after the first infusion of sipuleucel-T). The primary immune response analysis population will include all subjects who receive all 3 infusions of sipuleucel-T; summaries will also be generated for the population of patients who receive at least one partial infusion of sipuleucel-T. Logistic regression will be used to explore the effect of baseline characteristics on the primary endpoint. Repeated measurement mixed models will be used to explore the individual immune response assays as continuous endpoints over time. Transformation of the continuous outcome may be applied if the original data are not normally distributed. Key subgroups of interest will be defined on the basis of baseline demographics and disease characteristics (e.g., age, race, ECOG status, and serum PSA).

Table 1 summarizes the minimum detectable percent difference in immune responders with 90% power using a two independent proportions test at the two-sided 0.05-level between two subgroups, with the smaller subgroup representing 10% of total sample size and a minimum immune response incidence in each subgroup of 20% to 80%. In the IMPACT study, 79% of sipuleucel-T subjects had an immune response by any of the 3 assays to either PA2024 or PAP at any time point post-baseline (Sheikh 2013).

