## **5.0 STUDY DESIGN AND CONDUCT**

### **5.1 Study Design**

This study (P11-4) is a multicenter trial in men  $\geq 18$  years of age with prostate cancer who are enrolled in a Dendreon-sponsored trial or registry, or an IIT, and will receive sipuleucel-T. Men who meet these criteria and have not yet undergone leukapheresis for their first dose of sipuleucel-T are eligible to participate in P11-4. Subject accrual and study duration for P11-4 will depend on the timing and population of the concurrent trials.

For P11-4, cellular and humoral immune responses will be assessed from 60-mL blood samples (immune monitoring blood samples; 5x10 mL heparin whole blood tubes and 1x10 mL serum tube) obtained at baseline (defined for the purposes of P11-4 sample collection as any time after informed consent, but prior to leukapheresis for the first dose of sipuleucel-T), as well as 6, 10, 14, 26, 39, and 52 weeks after the first infusion of sipuleucel-T ([Figure 1](#); [Appendix 1](#)).

Figure 1: P11-4 Study Schematic

Abbreviation: AOR=additional optional research (blood samples for genomic and gene expression analyses, and other additional testing).

- a Prior to consenting to participate in P11-4, subjects must have consented to participate in another Dendreon-sponsored trial or registry, or IIT, in which they will receive sipuleucel-T, and must sign the informed consent form for P11-4 **prior to the first scheduled leukapheresis procedure and any blood sampling for P11-4.**
- b For each subject, participation in P11-4 may end prior to the collection of the week 52 immune monitoring and AOR blood samples if the subject withdraws from, or otherwise completes participation in, the concurrent trial.

As part of the normal manufacturing and quality control process, samples of cellular components from pre-culture and post-culture (sipuleucel-T) cells are used to confirm product quality attributes and potency (product characterization). Consent to participate in this study will allow unused portions of these pre- and post-culture samples, an additional 1% of the pre-culture cellular components, and immune monitoring blood samples to undergo additional analyses (e.g., flow cytometry or spectral analyses) to identify potential biomarkers of the immune response.

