**Table 1: Minimal Detectable Percentage of Immune Responders by Sample Size**

Total Sample Size	Sample Size per Subgroup	Immune Responders (Smallest % in Either Subgroup)	Minimum Detectable Difference (%)
1000	900/100	20%	15%
1000	900/100	50%	17%
1000	900/100	80%	12%
500	450/50	20%	22%
500	450/50	50%	23%
500	450/50	80%	16%
200	180/20	20%	36%
200	180/20	50%	35%
200	180/20	80%	20%

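### Does the 20% entry for 180/20 at 80% in Table 1 fail the stated 90% power because it sits at the 100% ceiling?

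*Combined protocol and SAP*

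**What the plan says.** Section 7.2.1 describes Table 1 as the "minimum detectable percent difference in immune responders with 90% power using a two independent proportions test at the two-sided 0.05-level between two subgroups". The setting is "with the smaller subgroup representing 10% of total sample size and a minimum immune response incidence in each subgroup of 20% to 80" per cent. The variant of the test is not named. The table's third column is labelled "Immune Responders (Smallest % in Either Subgroup"), so the lower rate may belong to the larger or the smaller subgroup.

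Table 1 has nine rows, with differences in whole percents. The row in question has a total of 200, subgroups 180/20, lower rate 80% and difference 20%. No footnote remarks on it.

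Three other statements give the context. Section 7.2.1 reports an earlier response rate beside the table: "In the IMPACT study, 79% of sipuleucel-T subjects had an immune response by any of the 3 assays to either PA2024 or PAP". The comparison that the table illustrates is exploratory: "Logistic regression will be used to explore the effect of baseline characteristics on the primary endpoint". Section 5.1 leaves enrolment open: "Subject accrual and study duration for P11-4 will depend on the timing and population of the concurrent trials".

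**The concern.** A minimum detectable difference should leave room above it. Here the higher rate is 80% + 20% = 100%, so the printed minimum is also the maximum. That suggests a calculation that ran out of room and printed the ceiling without saying so.

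A check by exact Pearson test seems to confirm it. Taking the less favourable direction in each row, the required differences round to all eight other entries, and only this row has no solution. In the other two 80% rows the match needs the smaller subgroup to be the higher one (12.0 and 15.7 points, against 11.3 and 14.4 the other way), which is the direction that falls short here.

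Table 1 is the protocol's only power statement, and its 80% rows lie nearest the quoted 79%. If the entry were wrong, a reader could believe that a study of 200 has 90% power for a subgroup difference when it does not.

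**Working it through.** **Inputs.** From Section 7.2.1 and Table 1: two-sided level 0.05 (critical value 1.960), target power 90%, subgroups 180 and 20, rates 80% and 100%. The test variant is an assumption, so several are shown.

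**1. The cell, smaller subgroup higher.** All 20 subjects respond. With x responders among 180, the Pearson statistic is z = (1 − x/180) / √[p̄(1 − p̄)(1/180 + 1/20)], where p̄ = (x + 20)/200.

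- x = 150: p̄ = 0.85, z = 1.980, reject.
- x = 151: p̄ = 0.855, z = 1.941, do not reject.

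Power = P(Bin(180, 0.8) ≤ 150) = 88.9%. Fisher's test has the same cut-off (p = 0.0485 at 150, 0.0856 at 151) and so the same power.

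**2. The cell, smaller subgroup lower.** Exact Pearson power is 98.8% and exact Fisher power 93.1%. Pearson needs 18.6 points for 90%.

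**3. All nine rows at their printed differences, exact Pearson power.**

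| Subgroups | Lower rate | Printed | Smaller higher | Smaller lower |
|---|---|---|---|---|
| 900/100 | 20% | 15% | 90.7% | **88.8%** |
| 900/100 | 50% | 17% | 91.0% | 91.4% |
| 900/100 | 80% | 12% | 90.2% | 93.6% |
| 450/50 | 20% | 22% | 91.6% | **89.3%** |
| 450/50 | 50% | 23% | **89.4%** | 90.5% |
| 450/50 | 80% | 16% | 92.0% | 96.1% |
| 180/20 | 20% | 36% | 92.5% | 90.4% |
| 180/20 | 50% | 35% | 90.7% | 93.5% |
| 180/20 | 80% | 20% | **88.9%** | 98.8% |

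Four entries fall just under 90% in one direction. The disputed one is not the lowest.

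**4. How much difference is missing.** In the other three low cells, 0.2 to 0.3 of a point more restores 90% (15.3, 22.3, 23.2). Here the higher rate cannot rise, but the lower rate can fall. With the smaller subgroup at 100% the cut-off stays at 150, so power is P(Bin(180, p) ≤ 150): 90.6% at p = 79.7%, and 93.9% at p = 79%, the rate quoted from IMPACT. The missing amount is again at most 0.3 of a point.

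**5. Other two-proportion tests at 20 points.**

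- Arcsine formula: h = 2·arcsin(√1) − 2·arcsin(√0.8) = 3.1416 − 2.2143 = 0.9273. Divide by √(1/180 + 1/20) = 0.2357 to get 3.934. Power = Φ(3.934 − 1.960) = 97.6%, the same in both directions. It needs 19.3 points for 90%.
- Exact arcsine test: at least 90% in both directions. The worse one needs about 19.5 to 19.6 points, which rounds to the printed 20%.
- Exact likelihood-ratio test: 99.99% with the smaller subgroup higher, 98.8% with it lower.

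**6. Which test produced the table?** Exact Pearson, worse direction, rounds to the other eight entries and gives no value for the ninth. The exact arcsine test, worse direction, rounds to seven of those eight (450/50 at 80% gives 15.4 against the printed 16) and to the ninth. Each accounts for eight of nine. The table does not identify its method.

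**The case for a change.** The strongest reply is that the other low cells can be repaired by a fraction of a point, while here no difference above 20 exists once the lower rate is fixed at 80%. Under Pearson or Fisher with the smaller subgroup higher, 90% is then out of reach, and power drops quickly below the ceiling (74.1% at 99% against 80%, exact Pearson). That is true as stated.

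The pooled normal formula looks worse. With p̄ = (144 + 20)/200 = 0.82, power is Φ[(0.20 − 1.960 × 0.0906)/0.0298] = 77.5%. It approximates the Pearson test, however, and exact enumeration of that test gives 88.9%. In the other direction the formula gives 93.5%.

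The tests that do reach 90% both ways can also be criticised: at a common rate of 80% in 180/20, the true type I error is 6.8% for arcsine and 5.8% for likelihood ratio, against 4.8% for Pearson. That is a fair comment on those tests in small samples. It does not show that the sponsor's calculation departed from a stated nominal level of 0.05. The planned analysis is logistic regression, whose likelihood-ratio test for one binary factor is the one that exceeds 90% in both directions.

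What stands is that the entry needs every subject in one subgroup to respond, that the table does not say so, and that the test is not named. These are omissions of detail.

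**Conclusion.** The concern does not hold. The entry falls short only under an assumed test (Pearson or Fisher) in one of two directions, and then by 90.0 − 88.9 = 1.1 points. That is in line with the rest of a table printed in whole percents, where another entry stands at 88.8% on the same basis. In the other direction, and under the arcsine and likelihood-ratio forms in both, 20 points gives more than 90%. The exact Pearson worse-direction rule that makes the entry look wrong appears nowhere in the plan and could not have produced a 20% here.

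The conclusion rests on taking the 0.05 level as nominal and on treating a power within about one point of 90% as agreement for whole-percent entries. If the sponsor confirmed that Pearson or Fisher was used, a note on direction and ceiling would be apt, but the practical reading would not change: accrual follows the concurrent trials, baseline effects are only explored, and no sample size or decision depends on this cell.
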